	
state) as determined in primary or current bioptic tumour specimen on tumour response
 
Tertiary objectives (in <math>^{177}\text{Lu}</math>-edotreotide patients)
 
 
1. To assess differences in tumour and kidney radiation dose estimates, obtained with conventional 2D (planar), compared to hybrid (2D/3D), and 3D (SPECT) imaging
 
2. To evaluate the value of pre-therapeutic SSTR imaging (SRI) to predict tumour response (globally/at lesion level)
 
3. To evaluate the relationship between PRRT radiation dose (in Gy) and tumour response (globally/at lesion level)
 
4. To assess metabolic stability and excretion pattern of <math>^{177}\text{Lu}</math>-edotreotide
 
5. To assess bone marrow radiation dose
 

Project code	ITM-LET-01
Investigational Medicinal Product (IMP)	$^{177}\text{Lu}$ -edotreotide, an octreotide-derived somatostatin analogue containing the chelator DOTA, radiolabelled with n.c.a. lutetium-177, a radio-lanthanide, emitting $\beta$ - and $\gamma$ -radiation.
Name of active ingredients	$^{177}\text{Lu}$ -edotreotide (synonyms, e.g.: $^{177}\text{Lu}$ -Edo, $^{177}\text{Lu}$ -DOTATOC)
Doses	A maximum of four cycles of $7.5 \pm 0.7$ GBq $^{177}\text{Lu}$ -edotreotide, each containing a mass dose of 150 $\mu\text{g}$ of DOTATOC. The cumulative $^{177}\text{Lu}$ -edotreotide dose will be up to 30 GBq, gauged individually not to exceed an absorbed dose of 23 Gy to the kidneys.
Route of administration	Slow intravenous infusion/injection (IV)
Duration of treatment	4 cycles, 90 ( $\pm 14$ ) days apart (total duration: 270 days/9 months)
Reference product (RP)	Everolimus, an mTOR inhibitor
Name of active ingredients	Everolimus
Doses	10 mg/d
Route of administration	Oral
Duration of treatment	Continuous daily treatment until diagnosis of progression or EOS
Indication	Treatment of patients with well-differentiated, somatostatin receptor-positive, unresectable or metastatic neuroendocrine tumors (NETs) of gastroenteric or pancreatic origin

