Everolimus: Patients randomised to everolimus therapy will undergo out-patient visits only. Patients will receive a standard dose of 10 mg daily, which may be reduced, where required for acceptable tolerability, according to manufacturer's product information (see [Appendix 4](#)).

Both study arms: Study visits will be monthly in the first 12 months, thereafter 3-monthly until end of study at month 30 or until progression (whatever occurs first). For symptom control, all patients are allowed to receive somatostatin analogues (SSA), as clinically indicated (best supportive care) in required doses, not to exceed licensed doses. In the  $^{177}\text{Lu}$ -edotreotide arm, clinically established wash-out periods prior to  $^{177}\text{Lu}$ -edotreotide dosing have to be considered (1 day for immediate release, and 28 days for sustained release SSA).

Safety, tolerability and symptom control parameters, as well as tumour markers are captured at regular intervals.

To assess efficacy, serial morphological imaging, comprising native liver and contrast-enhanced liver and 3 regional (pelvis, abdomen, thorax) MRI or CT (see Clinical Imaging Manual for details), is scheduled every three months, consistently using baseline methods. Evaluation of tumour response will be performed by local investigators using RECIST 1.1 criteria.

In case of clinically suspected tumour progression, investigators may schedule appropriate diagnostic imaging at any time.

Image analyses will also be conducted centrally. For establishment of PFS (primary endpoint) blinded reading in duplicate, with adjudication in case of discordance will be used.

Patients who progressed under everolimus may be offered  $^{177}\text{Lu}$ -edotreotide therapy based on the personal judgement of the Investigator, if he/she considers it appropriate and likely to be beneficial for the individual patient (see Section [7.4.2](#)).

To further evaluate tumour response, the tumour marker Chromogranin A (Cg-A) will be determined at baseline, and then monthly until month 12, thereafter in 3-monthly intervals until diagnosis of progression or end of study. Cg-A represents a secretory protein present in dense-core vesicles of neuroendocrine (NE) cells. It is being expressed in most secretory, but also non-functional NET. Cg-A is the best circulating neuroendocrine marker available up to now for the management of differentiated

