## 5.7 Treatment Compliance

A record of the number of  $^{177}\text{Lu}$ -edotreotide doses and everolimus tablets dispensed to and taken by each subject must be maintained and reconciled with study treatment and compliance records. Details of each study drug administration will be recorded in appropriate source documents and then reported in the CRF.

- $^{177}\text{Lu}$ -edotreotide:

$^{177}\text{Lu}$ -edotreotide will be administered by study personnel at the trial site only. In any case of interruption of  $^{177}\text{Lu}$ -edotreotide infusion, the infused and discarded amounts will be recorded.  $^{177}\text{Lu}$ -edotreotide is to be ordered on the day of randomisation. The first dose of  $^{177}\text{Lu}$ -edotreotide should be administered within 21 days of randomisation. In case of any delay, the site should check with the Sponsor via the site monitor and the reason for delay should be documented accordingly.

- Everolimus:

Subjects will be asked to maintain a dosing diary to record their daily administration of everolimus. At each visit, the subject should return the dosing diary. An evaluation of subject compliance with study treatments taken will be performed. The investigator will make every effort to bring non-compliant subjects into compliance. Compliance with dosing will be assessed through querying the subject during site visits and will be documented in the source documents and in the CRF, including treatment start and stop dates, dates for treatment delays and/or dose reductions.

The following deviations are defined as major protocol deviations, leading to exclusion from the PP set (see Section 9.3.3):

- $^{177}\text{Lu}$ -edotreotide arm:

- Subjects with incomplete  $^{177}\text{Lu}$ -edotreotide infusion, in which less than 50% of the total pre-scribed activity (GBq) based on initially dosimetry assessment was injected.
- Subjects in whom a dose was administered more than 30 days outside the per protocol date.

- Everolimus arm:
  - Subjects missing more than 14 doses, within a visit interval of 30 days (with exception of treatment interruptions due to toxicity, see Section 5.4.3.1).

Regardless whether a patient is compliant or non-compliant, the investigator must make every effort to perform all investigations according to the protocol for the entire duration of study participation.

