**7.3.9 Second Year**

During the second year of the study, patients in the everolimus arm continue on everolimus, while patients in the  $^{177}\text{Lu}$ -edotreotide arm will not receive further PRRT treatment until diagnosis of progression. Study visits during the 2nd year take place on an out-patient basis in 3-monthly intervals (12, 15, 18, 21, 24, and 27 months after day 0, with  $\pm 21$  day time window). For the management of patients impacted by the follow-up extension, see Section 3.1. Examinations comprise physical examination, vital signs, blood sampling for laboratory and tumour markers, pregnancy test, EORTC QLQ questionnaire, recording of AEs and concomitant medication, morphological MRI/CT imaging at every second year visit, as well as 12-lead ECG and  $^{99\text{m}}\text{Tc}$ -MAG3 renal scintigraphy at months 12, 18, and 24 only. Morphological MRI/CT imaging and  $^{99\text{m}}\text{Tc}$ -MAG3 renal scintigraphy should be performed within 7 days prior to the study visit, in order for the results to be available at the time of the visit. Pregnancy tests for the following months without visits at the study centre will be handed out to the patients at every visit. Blood-sampling can be performed up to 72 hours prior to each visit according to local practice and as clinically appropriate. Pregnancy tests are to be repeated monthly during year 2 until EOS. Everolimus patients continue to receive their patient diary at every visit.

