3.4 Study Variables

3.4.1 Primary Variable

Progression-free survival

Progression-free survival will be determined starting from randomisation until the date of an event (PD or death). For the primary analysis, any withdrawal (or drop-out) before EOS visit at month 30 will be censored. Patients who have not shown progression at the end of the study (30 months) will also be censored.

In more details, the following rules will be applied for the main PFS analysis:

ITM-LET-01	Statistical Analysis Plan
------------	---------------------------

Table 1: PFS analysis rules

Situation	Date of Progression or Censoring	Outcome
Tumour progression or death	Earliest date of PD or death	Event (PD or Death)
No tumour progression and not death	Date of last adequate* radiological assessment	Censored
Unless:		
No baseline radiological tumour assessment	Date of randomisation	Censored
No adequate post-baseline radiological assessment and date of death, if any, is after 2 or more scan intervals following randomization**	Date of randomisation	Censored
New anticancer treatment started prior to tumour progression or death (whichever is earlier)	Date of the last adequate radiological assessment prior to start of new anticancer treatment or date of randomization (whichever is later)	Censored
Tumour progression or death documented immediately after 2 or more consecutive missing scan** following last adequate radiological tumour assessment or randomization (whichever is later).	Date of last adequate radiological tumour assessment or date of randomisation (whichever is later).	Censored

Table footnotes:

**Adequate radiological tumour assessment refers to an assessment with one of the following responses: CR, PR, SD, or PD.*

***The interval is higher than 2 times the maximal protocol scheduled RECIST 1.1 assessment interval (i.e. >222 days = 2*(90+21))*

For primary endpoint (PFS) main analysis, post-randomisation tumour assessment based on blinded central review compare to baseline will be used.

Where appropriate, sensitivity analyses will explore the impact of the chosen approaches and data issues observed during the blind review on the study results. These could include but not limit to:

- Blinded central RECIST 1.1 evaluation (main analysis) vs. Local RECIST assessments
- Applied main PFS censoring rules (main analysis, see Table above) vs. different approaches (e.g. next scheduled assessment date instead of date of radiological

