For the sample size calculations, i.e. estimating the sample size, the power and/or the effect size, the following considerations were taken into account:

With regard to PFS, a two-sided logrank test with an overall sample size of $N=242$ subjects (180 events; randomised 1 : 2, $N_1=80$ subjects [68 events] in the everolimus group and $N_2=162$ subjects [112 events] in the ^{177}Lu -edotreotide group) achieves 80% power at a 5% significance level to detect a hazard ratio (HR) of 0.6471 when the everolimus group median survival time is 11 months (i.e., a difference of an additional 6 months in the ^{177}Lu -edotreotide group). The study was planned to last for 48 months of which subject accrual occurs in the first 24 months. The accrual across time is uniform. Of note, the trial sample size was not revised (i.e. decreased) after the protocol amendment that extended the patient follow-up from 24 months to 30 months.

Based on this HR a total sample size of 300 will compensate for a dropout rate (censored data) of 15% for primary endpoint analysis.

With regard to overall response rates, group sample sizes of 200 in the ^{177}Lu -edotreotide group and 100 in the everolimus group achieve 89% power to detect an odds ratio between the group ORRs of 4.2 (that corresponds to rates of 5% and 18%). The proportion in the ^{177}Lu -edotreotide group is assumed to be 5% under the null hypothesis and 18% under the alternative hypothesis. The proportion in the everolimus group is assumed to be 5% according to results of the RADIANT-3 study (Yao et al., 2011). The test statistic used is the two-sided Fisher's Exact Test. The significance level of the test is 5%. A dropout rate of 15% is included in this calculation using PASS software.

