6.2 Protocol Deviations

As per current protocol (see Protocol Section 9.3.2), for the study arms at least the following protocol deviations are defined as major protocol deviations which should lead to PP set exclusion

- ¹⁷⁷Lu-edotreotide arm:
 - Subjects with incomplete ¹⁷⁷Lu-edotreotide infusion, in which less than 50% of the total pre-scribed activity (GBq) based on initially dosimetry assessment was injected.
 - Subjects missing more than two scheduled doses, or in whom doses were administered more than 30 days outside the date, specified per protocol.
- Everolimus arm:
 - Subjects missing more than 14 doses, within a visit interval of 30 days (with exception of treatment interruptions due to toxicity (see protocol Section 5.4.2)).

Decisions on all Serious Protocol deviations which lead to PP set exclusion will be taken on an ongoing basis according to the Protocol Deviation Plan, confirmed at the blind data review meetings and finalised before analysis. Protocol deviations and the resulting exclusions from the PP set will be summarised and listed in a frequency distribution table.

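### The everolimus per-protocol rule makes exclusion depend on time on drug, so controls with longer PFS are excluded disproportionately, and the rule has no defined meaning after month 12

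*Protocol*

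**What the plan says.** The everolimus criterion in Protocol 5.7 is "Subjects missing more than 14 doses, within a visit interval of 30 days (with exception of treatment interruptions due to toxicity", followed by a section reference that closes the bracket. Protocol 9.3.3.2 repeats it. SAP 6.2 carries it forward under the statement that "at least the following protocol deviations are defined as major protocol deviations which should lead to PP set exclusion". None of the three places limits how many intervals are examined, sets an overall adherence level, or fixes an assessment window.

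Time on everolimus is given in the Protocol Synopsis: "Continuous daily treatment until diagnosis of progression or EOS". The visit schedule is in Protocol 3.1: "Study visits will be monthly in the first 12 months, thereafter 3-monthly until end of study at month 30 or until progression". Protocol 7.3.9 confirms this for the later period: "Study visits during the 2nd year take place on an out-patient basis in 3-monthly intervals".

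For the PRRT arm, all three places exclude patients who received less than half of the prescribed activity or who had a dose more than 30 days off schedule. Protocol 9.3.3.2 and SAP 6.2 also exclude patients who missed more than two scheduled doses.

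The PP analysis is described as an additional analysis to detect bias in the Full Analysis Set (FAS) result (Protocol 9.3.3.2, SAP 5.2.2). The confirmatory tests use the FAS (Protocol 9.3.3.1, SAP 5.2.1).

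**The concern.** A control who progresses at 3 months passes through 3 intervals in which the rule can be triggered; one still progression-free at month 12 passes through 12. A single bad interval deletes the patient's whole PFS time. PP membership therefore depends on the outcome, even when missed doses have nothing to do with prognosis. Losing more of the longer PFS times shortens the PP control curve, which on its own favours PRRT. That is an unwelcome property in an analysis meant to check the FAS for bias.

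Non-toxicity gaps are not hypothetical: SAP 6.7 lists COVID-related delays in drug shipping among the reasons for deviations, and the rule does not exempt them.

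Separately, the schedule contains no 30-day visit interval from month 12 to month 30. The rule could lapse. It could be applied in rolling 30-day windows. Or it could be applied to each interval of about 90 days, where 15 missed doses is 15/90 = 17% rather than 15/30 = 50%. These readings give different PP sets. This gap needs no assumed rate.

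**Working it through.** **Inputs from the documents.** Control median PFS is 11 months (SAP Section 4: "when the everolimus group median survival time is 11 months"). Follow-up is capped at 30 months (SAP 3.4.1: "Patients who have not shown progression at the end of the study (30 months) will also be censored"). Allocation is 2:1, with 180 events. **Assumed:** the probability q of a non-toxicity breach per 30-day interval, which the documents do not give; the range used is 0.25% to 5%.

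**The plan's own figure.** SAP Section 4 states that the PFS design "achieves 80% power at a 5% significance level to detect a hazard ratio (HR) of 0.6471". With 180 events at 2:1, SE(log HR) = 1/√(180 × 1/3 × 2/3) = 0.158. |ln 0.6471| = 0.435, and 0.435/0.158 − 1.96 = 0.79, giving power of 78.6%. This is within 2 points of the stated 80%. (The Schoenfeld formula asks for 187 events for 80%.) The design medians are therefore usable. The plan states no figure for PP exclusions.

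**Chance of exclusion.** After k completed intervals, P = 1 − (1 − q)^k. At q = 1%:

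| Intervals k | 3 | 12 | 24 | 30 |
|---|---|---|---|---|
| P(excluded) | 3.0% | 11.4% | 21.4% | 26.0% |

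On the literal wording k stops at 12. The last two columns apply only if 30-day windows continue to month 30.

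**Effect on the PP hazard ratio.** The simulation uses exponential PFS, a 30-month cap, breaches independent of prognosis, no PRRT exclusions and a true HR of 1.00:

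| q per interval | Months 0–12 only | Windows to month 30 |
|---|---|---|
| 0.25% | 0.99 | 0.97 |
| 0.5% | 0.98 | 0.95 |
| 1% | 0.96 | 0.90 |
| 2% | 0.93 | 0.81 |
| 5% | 0.82 | 0.60 |

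Further results at q = 1%:

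| | Months 0–12 only | Windows to month 30 |
|---|---|---|
| Excluded, PFS under 6 months | 2.3% | 2.3% |
| Excluded, PFS 24 months or more | 11.4% | 25% |
| Excluded, all controls | 7.8% | 11.8% |
| PP control median (months) | about 10.4 | 9.7 |
| PP HR when the true HR is 0.647 | 0.625 | 0.583 |

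**Hand check.** With a constant breach rate v, retained controls have hazard λ + v. Here λ = ln 2/11 = 0.063 per month. Adding 0.010 gives 0.073, and ln 2/0.073 = 9.5 months. This is close to the simulated 9.7, where only completed intervals count.

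**Adding the PRRT late-dose rule.** Doses 2 to 4 go only to patients still progression-free, so exposure to this rule also grows with PFS. With an assumed late-dose breach of 2, 3 or 5% per dose, and everolimus at 1% over months 0 to 12, the null HR moves from 0.96 to 0.98, 0.99 and 1.01. With everolimus at 0.5% and 2% per PRRT dose it is 1.00. If everolimus windows run to month 30, the same PRRT rates offset the 1% case only in part.

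**The case against.** The strongest reply is that the size is unknown and may be small. A breach means missing about half a month's tablets for reasons other than toxicity, and nothing in the documents says how often that happens. On the literal wording, a control with PFS of 13 months and one with 30 months face the same risk. An HR of 0.96 is a shift of |ln 0.96|/0.158 = 0.26 standard errors at 180 events. All of this stands.

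A reader might infer that the PP analysis favours PRRT by construction. The documents do not support that. The PRRT arm has its own single-event rule with exposure that grows with time progression-free, so the net sign depends on two unknown rates. Under one reading of Protocol 5.4.3.2, a permitted toxicity delay (week 16 plus 2 weeks, day 126) falls 36 days after day 90 and so beyond the 30-day limit; those passages should be reconciled. The simulation also assumes that missed doses do not affect PFS. If they shorten it, removing poor adherers could lengthen the control curve.

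A reader might also infer that long-PFS controls disappear from the PP set. They do not: at 1% per interval, about 75% of those with PFS of 24 months or more remain even with every window to month 30 counted.

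Finally, SAP 6.2 refers PP decisions to a Protocol Deviation Plan and blind data review meetings, with exclusions summarised and listed. That plan is not among the documents and may settle the rule after month 12. It would not remove the dependence on time on drug that the stated rule creates.

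**Conclusion.** The point holds as a defect in the definition of a supportive analysis set. For any breach rate above zero that is unrelated to prognosis, the everolimus rule excludes longer-PFS controls disproportionately. Taken alone, at assumed rates of 0.5 to 2% per interval, it pulls the PP HR to between 0.98 and 0.93 on the literal wording; the lower values of 0.95 to 0.81 need 30-day windows to month 30, which the text does not establish. The net effect after PRRT exclusions cannot be determined from the documents. The missing definition after month 12 stands without any assumption.

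It would be wrong to infer that the primary result is at risk: the confirmatory PFS, ORR and OS tests, their alpha and their power rest on the FAS and are untouched. The practical consequence is that a PP result agreeing with the FAS, or stronger than it, could be over-read as reassurance. The change is worth making.

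**What to change.** In Protocol 5.7 and 9.3.3.2 and SAP 6.2, replace the single-interval criterion for PP membership with an adherence proportion over the whole time on treatment. For example, exclude a control who took less than 50% of prescribed everolimus doses according to the dosing diary, not counting interruptions due to toxicity. This works the same way before and after month 12. Tabulate PP exclusions by arm and by PFS time so that any remaining imbalance is visible.

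The proportion rule is not perfectly neutral: one bad month can now exclude only a control with short time on drug. The effect is negligible. With 22 missed doses per bad interval and a 1% rate, under 1% of controls with PFS below 2 months are excluded and practically none beyond 6 months, and the null HR is about 1.00. If single breaches must still count, an alternative is to keep the patient and censor PP PFS at the last adequate scan before the breach (null HR 0.98 to 1.00).

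The cost is wording in three places and one derivation from diary data already collected, with a slightly more inclusive PP set. The same edit can align the PRRT lists, since Protocol 5.7 omits the missed-doses criterion found in the other two places. Only the definition of the analysis set changes, not dosing or patient management.

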## 5.8 Treatment of Overdose

- Lu-edotreotide:

Lu-edotreotide has a very favourable safety profile (see Section 1.3).

The risk of overdosing is minimal in this trial, as individual doses will be prepared centrally by a radiopharmaceutical contract manufacturer. Nevertheless, if accidental overdosing of radio-labelled product should occur, it will result in increased radioactive tissue exposure, with kidney and bone marrow as the critical organs.

In the event of an overdose of Lu-edotreotide, no specific treatments are available, and the patient should be treated at the discretion of the investigator.

- Everolimus:

Reported experience with overdose in humans is very limited. Single doses of up to 70 mg have been given with acceptable acute tolerability (EU: SmPC, Afinitor®, current version). General supportive measures should be initiated in all cases of overdose.

## 6 Therapies other than Study Drug

### 6.1 Prior and Concomitant Therapy

Prior medications (up to 4 weeks prior to the screening visit) and all medications taken from baseline until EOS (including herbal products) must be recorded in the patient's file. The indication for each drug, generic name, dosage form, strength, dose, frequency of dosing, route of administration, start date and, if applicable, stop date should also be recorded in the CRF. All medications will be encoded according to WHO-DD classification.

